11. MANAGEMENT AND REPORTING OF SAFETY INFORMATION

11.1. Adverse Events

An **adverse event** (AE) is any untoward medical occurrence in a clinical study subject administered a pharmaceutical product, which does not necessarily have a causal relationship with the treatment. An AE can therefore be any unfavorable and/or unintended sign, symptom, or disease temporally associated with the use of a medicinal product, whether or not considered related to the medicinal product. AEs may also include lack of efficacy, overdose, drug abuse/misuse reports, or occupational exposure. Preexisting events that increase in severity or change in nature during or as a consequence of participation in a clinical study are also considered AEs.

As this is a retrospective, non-interventional study not all medical events noted in the subject's medical records will be collected. However, where recorded in the subject's medical notes, adverse events that occur during the period under review and that are associated with a Gilead drug will be captured. These are known as adverse drug reactions, as defined in section 11.1.1

11.1.1. Adverse Drug Reactions

An **adverse drug reaction** (ADR) is defined as an untoward medical occurrence (unintended or noxious responses) considered causally related to an investigational or approved medicinal product at any dose administered. Adverse reactions may arise from medication errors, uses outside what is foreseen in the protocol or prescribing information (off-label use), misuse and abuse of the product, overdose, or occupational exposure.

11.1.2. Serious Adverse Events

A serious adverse event (SAE) is defined as an event that, at any dose, results in the following:

Death

Life-threatening (Note: The term "life-threatening" in the definition of "serious" refers to an event in which the subject was at risk of death at the time of the event; it does not refer to an event that hypothetically might have caused death if it were more severe.)

In-patient hospitalization or prolongation of existing hospitalization

Persistent or significant disability/incapacity

A congenital anomaly/birth defect

A medically important event or reaction: such events may not be immediately life-threatening or result in death or hospitalization but may jeopardize the subject or may require intervention to prevent one of the other outcomes constituting SAEs. Medical and scientific judgment must be

exercised to determine whether such an event is a reportable under expedited reporting rules. Examples of medically important events include intensive treatment in an emergency room or at home for allergic bronchospasm; blood dyscrasias or convulsions that do not result in hospitalization; and development of drug dependency or drug abuse. For the avoidance of doubt, infections resulting from contaminated medicinal product will be considered a medically important event and subject to expedited reporting requirements.

A Serious Adverse Drug Reaction (SADR) is an Adverse Drug Reaction that meets the criteria for being serious as detailed above.

In this study we are only collecting adverse drug reactions and serious adverse drug reactions that occur during the period under review and that are associated with a Gilead drug.

Clarification of Serious Adverse Events

Complications that occur during hospitalizations are AEs. If a complication prolongs the hospitalization, is life-threatening, or meets any of the other definitions of an SAE, then it is an SAE.

"In-patient hospitalization" means the subject has been formally admitted to a hospital for medical reasons, for any length of time. This may or may not be overnight. It does not include presentation and care within an emergency department.

The investigator should attempt to establish a diagnosis of the event on the basis of signs, symptoms, and/or other clinical information. In such cases, the diagnosis (and not the individual signs/symptoms) should be documented as the AE and/or SAE.

A distinction should be drawn between seriousness and severity of AEs. Severity is a category utilized for rating the intensity of an event; both AEs and SAEs can be assessed for severity. An AE is defined as "serious" when it meets one of the predefined outcomes described above.

11.1.3. Clinical Laboratory Abnormalities and Other Abnormal Assessments as Adverse Events or Serious Adverse Events

Laboratory abnormalities without clinical significance are not recorded as AEs or SAEs. However, laboratory abnormalities (e.g., clinical chemistry, hematology, and urinalysis) that require medical or surgical intervention or lead to drug interruption, modification, or discontinuation that are deemed to be related to a Gilead drug must be recorded as an ADR (both serious and non-serious, if applicable. In addition, laboratory or other abnormal assessments (e.g., electrocardiogram, x-rays, vital signs) that are associated with signs and/or symptoms and related to a Gilead drug must also be recorded as an ADR (both serious and non-serious) if they meet the definitions as described in Sections 11.1.1 and 11.1.2. If the laboratory abnormality is part of a syndrome, record the syndrome or diagnosis (e.g., anemia), not the laboratory result (i.e., decreased hemoglobin).

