7.2. Rationale

The aim of this study is to evaluate the potential benefits of STR on two types of medication errors – one at the patient level (adherence) and one at the Healthcare provider level (prescription errors):

- To evaluate whether use of an STR can enhance adherence, assessing its clinical and economic consequences, in the European context,
- To quantify prescription errors and identify those that can be avoided by the use of STRs.

Adherence has generally been reported as either the level of adherence to a single component of a multi-drug regimen or as the average level of adherence to multiple components {27754}. Nonetheless, inadequate adherence may take two forms: non-adherence (NA), defined as not taking any of the regimen's components, and selective adherence (SA), defined as taking some but not all of the regimen's components. Whenever NA or SA occurs, the patient cannot be considered to fully adhere to ART and as such, overall inadequate adherence (OIA) may be defined as the sum of NA and SA.

Among the predictors of SA, CD4 lymphocyte count {27753}{27753}, adverse drug events {27753} regimen complexity (number of daily intakes, absence of fixed-dose combination, number of drug components) {27766} {21957} {27767} {27753} {27754} and ART medication errors {27744} have been identified. ART prescription and dispensing by non-specialists and tight stock management (especially in a context of economic constraints) may also contribute to SA but no studies have yet been published on these themes.

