11.2. Assessment of Adverse Events and Serious Adverse Events

The investigator or qualified sub investigator is responsible for final review and confirmation of accuracy of event information and assessments. Only ADRs and SADRs will be collected from the medical records. Events that the investigator considers to be related to a Gilead drug and that occur during the period of review should be recorded on the eCRF.

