11.3.2.2. Reporting Other Special Situations

All other special situation events that are captured in the medical notes of the subject during the period under review must be reported on the Gilead Non-Interventional Study Special Situation Report Form (appendix 1) and forwarded to Gilead DSPH within 24 hours of knowledge of the event. These reports must consist of situations that involve Eviplera, Stribild or Atripla and any other Gilead medication, but do not apply to non-Gilead medications.

11.4. Investigator Requirements and Instructions for Reporting Adverse Events and Serious Adverse Events to Gilead

All SADRs associated with Eviplera, Stribild or Atripla, or any other Gilead drugs, that occur during the period under review, will be recorded on the Gilead Non-Interventional Study

AE/SAE Study Report Form (appendix 1) and will be reported to Gilead DSPH within 24 hours of knowledge of the event. ADRs associated with Eviplera, Stribild or Atripla, or any other Gilead drugs, that occur during the period under review, will be recorded on the eCRF only.

SADR/SSR reports should be forwarded to the Gilead DSPH email address or fax below:

DSPH Representative:	[contact]	
	E-mail: [contact]	

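### Adverse drug reactions are recorded under a rule that differs by cohort, and nothing keeps them out of the propensity score or the adjusted models

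*Protocol*

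**What the plan says.** **What is recorded.** Protocol Section 11.1 limits capture to events "where recorded in the subject's medical notes, adverse events that occur during the period under review and that are associated with a Gilead drug". Section 11.1.2 states that "we are only collecting adverse drug reactions and serious adverse drug reactions that occur during the period under review"; its sentence goes on to limit these to reactions tied to a Gilead product. Section 11.2 makes this the rule for the eCRF, in a sentence beginning "Events that the investigator considers to be related to a Gilead drug and that occur during the period of review should be recorded on the". Section 11.1.3 applies the same limit to laboratory abnormalities.

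**Which drugs are Gilead drugs.** Section 11.4 refers to "ADRs associated with Eviplera, Stribild or Atripla, or any other Gilead drugs, that occur during the period under review", which places the three STRs among the sponsor's products. They are also the only STRs named in the sampling rules of Section 9.3. Non-STR regimens are multi-pill once-daily combinations of two NRTI plus an NNRTI or a boosted PI, with no restriction by manufacturer. Section 11.3.2.2 says of special-situation reports that they apply to Gilead medication "but do not apply to non-Gilead medications", so the protocol expects products from other makers to be in use.

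**How collected variables are used.** The synopsis, under Variables, treats everything collected as a confounder, apart from the dependent variable of the endpoint and variables related to it. Table 2 in Section 9.4 lists adverse drug reactions among the variables to collect. The synopsis, under Data Analysis, builds the propensity score from baseline and other retrospective information and excludes only measures of adherence. Step 1 of the matching procedure in Section 9.3 chooses covariates by statistical criteria and gives the strength of association with STR as the example. Section 9.8 then enters the propensity score in the outcome regression alongside the ART class.

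**The concern.** A variable used to match or adjust two cohorts should mean the same thing in both and should not be a consequence of the exposure. Adverse drug reactions fail on both counts here.

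First, any reaction attributed to a named STR is eligible for the eCRF. A reaction attributed to a non-Gilead component of a multi-pill regimen is not. The recording rule alone therefore creates an association with STR.

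Second, a reaction to the regimen under analysis arises after that regimen has started. It may lie on the route from regimen to adherence. Section 7.2 lists predictors of selective adherence ("Among the predictors of SA, CD4 lymphocyte count" opens the list) and includes adverse drug events among them.

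At stake is the covariate set behind the adjusted odds of more than 90% adherence, and behind the adjusted secondary endpoints on viral suppression, hospitalization and cost. Section 9.10 on limitations mentions neither the recording rule nor its consequence.

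**Working it through.** The protocol states no reaction rate and no related figure, so there is nothing to reproduce. The check sets the provisions side by side and adds one line of algebra.

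**1. Does eligibility differ by cohort?**
- STR patient-regimen: a reaction attributed to Eviplera, Stribild or Atripla is attributed to a Gilead drug, so it is always eligible (Sections 11.1.2, 11.2, 11.4).
- Non-STR patient-regimen: it is eligible only if attributed to a Gilead component.
- Reactions to non-Gilead co-medication are ineligible in both cohorts and create no difference.
- A subject may contribute regimens to both cohorts (Section 9.3), so the asymmetry works at the level of the patient-regimen, which is the unit of analysis.

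**2. How large could the artefact be?** Let r be the true reaction rate per patient-regimen, equal in both cohorts. Let c be the chance that a reaction is documented in the notes, also equal. Let f be the share of non-STR reactions attributed to a Gilead component.
- Recorded rate, STR: c × r
- Recorded rate, non-STR: c × f × r
- Recorded ratio: (c × r) / (c × f × r) = 1/f

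The documents do not give f. For assumed values:

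| f (assumed) | Recorded STR : non-STR ratio |
|---|---|
| 1.00 | 1.00 |
| 0.75 | 1.33 |
| 0.50 | 2.0 |
| 0.25 | 4.0 |

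The ratio is 1 only if every non-STR reaction is attributed to a Gilead component.

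**3. Can the variable reach the analysis?**
- Synopsis, Variables: all collected variables are confounders, except the dependent variable and related ones. For the adherence endpoint a reaction is neither.
- Section 9.4, Table 2: adverse drug reactions are collected.
- Synopsis, Data Analysis: only adherence measures are barred from the propensity score.
- Section 9.3, step 1: association with STR counts in favour of selecting a covariate. By step 2 of this check, the recording rule alone can produce that association.
- Section 9.8: the propensity score enters the outcome model, so whatever shapes the score affects both matching and adjustment.

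No provision breaks this chain.

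**4. Is it a valid covariate otherwise?** A reaction to the regimen under analysis follows exposure, so complete recording would not make it a baseline confounder. A reaction to an earlier regimen could precede the current one, but it is recorded under the same Gilead-only rule.

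**The case against.** The strongest reply has three parts.

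**Adverse drug reactions are not an endpoint.** Objectives and endpoints cover adherence, virological outcome, resistance, hospitalization, costs and prescription errors. Section 11 is a pharmacovigilance section and states openly that not all medical events will be collected. This stands. A reader might infer that the study will make STRs look less well tolerated, but the protocol plans no reaction frequency by cohort. A reader might also infer that reactions are fully captured in the STR cohort. They are only fully eligible: Section 11.1 makes capture depend on the medical notes, and Section 11.2.1 takes causality as documented there. Nor do Tables 2 and 3 impose the restriction; they hold relation to a Gilead drug as a field, and the filter comes from Section 11.

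**The confounder rule cannot be meant literally.** Read literally it would also take in refill dates and last menstrual period. Table 2 separates baseline and regimen-initiation characteristics from adverse drug reactions, and Section 9.6 assumes only 10 covariates. That makes it plausible that reactions were never intended as covariates. But the written rule includes them, the propensity score rule does not exclude them, and the selection criterion favours them. Intention needs to be stated.

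**The link to selective adherence is background.** Sections 7.1 and 7.2 report earlier studies, and no endpoint models selective adherence on reactions. This also stands; the link shows only why the variable might be thought worth adjusting for.

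**Conclusion.** The point holds as a gap in the adjustment rules. Eligibility for recording differs by cohort, and the protocol's own covariate rules would admit the variable to matching and to the adjusted models for the primary and secondary endpoints.

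It does not follow that the primary adherence comparison is invalid. Whether reactions enter depends on the covariate selection, and neither the direction nor the size of any effect on the adherence odds ratio can be derived from the documents. The ratio 1/f describes only the recorded reactions and is illustrative.

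Two assumptions carry the conclusion. Some non-STR components must be non-Gilead products; the protocol does not name their makers, but it sets no manufacturer restriction and refers to non-Gilead medications. The synopsis confounder rule must be applied as written. If both cohorts took only Gilead components, f would be 1 and the recording artefact would vanish, but the post-exposure problem would remain.

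**What to change.** 1. In the synopsis confounder rule, and in Sections 9.3 and 9.8, state that adverse drug reactions are excluded from the propensity score and from every STR versus non-STR model.
2. In Sections 9.8 and 9.10, state that these data are collected for sponsor pharmacovigilance only, that eligibility for recording differs by cohort, and that they will not be compared between cohorts.

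This is a few sentences. It changes no data collection and no safety reporting. As a protocol modification it needs ethics committee approval under Section 12.2.1.

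Recording reactions to every antiretroviral component, with a suspect-drug field, is optional. It is needed only if a description of reactions by cohort is wanted. It would add attribution review of up to five years of notes for about 700 + 805 = 1,505 subjects, and it would not make reactions a valid adjustment variable, so item 1 would still be required.

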11.2. Assessment of Adverse Events and Serious Adverse Events

The investigator or qualified sub investigator is responsible for final review and confirmation of accuracy of event information and assessments. Only ADRs and SADRs will be collected from the medical records. Events that the investigator considers to be related to a Gilead drug and that occur during the period of review should be recorded on the eCRF.

11.2.1. Assessment of Causality for Study Drugs

Since this is a retrospective study the investigator should note the relationship to a Gilead product as documented in the subject's medical notes. In general, the assessment of the relationship to drug therapy is based in the following considerations:

No: Evidence exists that the AE has an etiology other than the drug. For SAEs, an alternative causality must be provided (e.g., preexisting condition, underlying disease, intercurrent illness, concomitant medication).

Yes: There is a reasonable possibility that the event may have been caused by the medicinal product.

It should be emphasized that ineffective treatment should not be considered as causally related in the context of AE reporting.

11.3. Special Situations Reports

11.3.1. Definitions of Special Situations

Special situation reports include reports of pregnancy; medication error, abuse, misuse, or overdose; lack of effect; adverse reactions in infants following exposure from breastfeeding; and adverse reactions associated with product complaints and occupational exposure. A pregnancy report is used to report any pregnancy that occurred during the period under review.

Medication error is any unintentional error in the prescribing, dispensing, or administration of a medicinal product while in the control of the health care provider, subject, or consumer.

Abuse is defined as persistent or sporadic intentional excessive use of a medicinal product by a subject.

Misuse is defined as any intentional and inappropriate use of a medicinal product that is not in accordance with the protocol instructions or the local prescribing information.

An overdose is defined as an accidental or intentional administration of a quantity of a medicinal product given per administration or cumulatively which is above the maximum recommended dose as per protocol or in the product labelling (as it applies to the daily dose of the subject in question). In cases of a discrepancy in drug accountability, overdose will be established only when it is clear that the subject has taken the excess dose(s). Overdose cannot be established

when the subject cannot account for the discrepancy except in cases in which the investigator has reason to suspect that the subject has taken the additional dose(s).

Lack of effect is defined as the failure of the expected or intended pharmacologic action or therapeutic effect as described in the pharmacology and/or indications section of the current product labelling.

Product complaint is defined as complaints arising from potential deviations in the manufacture, packaging, or distribution of the medicinal product.

Occupational exposure is defined as exposure to a medicinal product as a result of one's professional or non-professional occupation.

11.3.2. Instructions for Reporting Special Situations

11.3.2.1. Instructions for Reporting Pregnancies

All pregnancies that occur during the period under review and the outcome of the pregnancy where recorded in the medical notes are to be reported to Gilead DSPH using the Pregnancy Report Form once they have been identified in the subject's medical record.

The pregnancy itself is not considered an AE nor is an induced elective abortion to terminate a pregnancy without medical reasons.

Any premature termination of pregnancy (e.g., a spontaneous abortion, an induced therapeutic abortion due to complications or other medical reasons) where reported in the medical notes must be reported as an SAE. The underlying medical reason for this procedure should be recorded as the AE term.

A spontaneous abortion is always considered to be an SAE and will be reported as described in Section 11.4.

The outcome, where available, should be reported to Gilead DSPH using the Pregnancy Outcome Report Form.

11.3.2.2. Reporting Other Special Situations

All other special situation events that are captured in the medical notes of the subject during the period under review must be reported on the Gilead Non-Interventional Study Special Situation Report Form (appendix 1) and forwarded to Gilead DSPH within 24 hours of knowledge of the event. These reports must consist of situations that involve Eviplera, Stribild or Atripla and any other Gilead medication, but do not apply to non-Gilead medications.

11.4. Investigator Requirements and Instructions for Reporting Adverse Events and Serious Adverse Events to Gilead

All SADRs associated with Eviplera, Stribild or Atripla, or any other Gilead drugs, that occur during the period under review, will be recorded on the Gilead Non-Interventional Study

AE/SAE Study Report Form (appendix 1) and will be reported to Gilead DSPH within 24 hours of knowledge of the event. ADRs associated with Eviplera, Stribild or Atripla, or any other Gilead drugs, that occur during the period under review, will be recorded on the eCRF only.

SADR/SSR reports should be forwarded to the Gilead DSPH email address or fax below:

DSPH Representative:	[contact]	
	E-mail: [contact]	

11.5. Investigator and Sponsor Reporting Requirements

Gilead is responsible for reporting and analyzing reports of all AEs and SAEs, serious adverse drug reactions (SADRs), or suspected unexpected serious adverse reactions (SUSARs), and special situation reports (SSRs) as determined by country-specific legislation or regulations where the study is conducted and other applicable countries. Gilead may be required to report to other regulatory agencies.

Assessment of expectedness for AEs, SAEs and SSRs will be determined by Gilead using reference safety information specified in the relevant local label.

12. RESPONSIBILITIES / PLANS FOR DISSEMINATING STUDY RESULTS

12.1. Investigator Responsibilities

12.1.1. Study Files and Retention of Records

The investigator must maintain adequate and accurate records to enable the conduct of the study to be fully documented. These documents should be classified into at least the following two categories: (1) investigator's study file, and (2) subject clinical source documents.

The Investigator's study file will contain the protocol/amendments, IEC approval, informed consent, and other appropriate documents. These study files shall be archived for at least 2 years after the last patient was documented by the Investigator. They shall retain the documents for a longer period, where so required by other applicable requirements or by an agreement between the sponsor and the investigator.

The subject clinical source documents consist of the usual patient files kept at the site of the Investigator and falls within the local regulations for such files and documents.

